6.4 Safety analyses

All safety summary tables, figures and listings will be based on the SAS unless otherwise specified.

6.4.1 Extent of exposure

IMP exposure

Exposure will be assessed by calculating difference between the number of doses dispensed and the number of doses returned. Returned doses were counted by counting unopen foil bags and multiplying by number of doses in a bag (5 doses in a foin bag) Accountability by an investigator is performed at V3 (1st off-season), V4 (1st pre-EGPS), V5 (1st on-seasons), V6 (2nd off-seasons), V7 (2nd pre-EGPS), V8 (2nd on-season) and V9 (end of trial). The number of doses taken will be summarised by treatment group.

IMP duration

The duration of treatment for each subject will be calculated from the date of randomisation up until and including the date of the last IMP intake. Treatment duration will be summarised by treatment group.

IMP compliance

IMP compliance (%) will be assessed as the number of doses taken divided by the treatment duration multiplied by 100. As IMP exposure will be counted without taken into account dosses lost, thus IMP compliance will be capped to 100%. IMP compliance will be summarised by treatment group.

eDiary compliance

eDiary compliance will be summarised by treatment group and year. Here, compliance is calculated separately for the daily entries (TCS) and the weekly entries (RQLQ). Compliance is calculated as the number of actual entries to the number of intended entries. For subjects withdrawing from the trial, their withdrawal date (if during the EPGS) will serve as the cut-off when calculating the number of intended entries.

IMP interruption

IMP interruption is defined as if IMP intake is interrupted for more than 7 days and not in relation to an AE. Number of subjects that have IMP interruptions, number of IMP interruptions will be summarised by treatment group and year.

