4.2 Exclusion criteria

Subjects are excluded from the trial if any of the following criteria apply:

- E1. Previous participation in this trial. Participation is defined as screening
- E2. Has a clinically relevant history of symptomatic seasonal and/or perennial allergic rhinoconjunctivitis and/or asthma caused by an allergen other than grass pollen, to which the subject is exposed, which could potentially overlap with the efficacy assessment periods
- E3. Within the last 3 months before the randomisation visit, has had an occurrence of any clinical deterioration of asthma that resulted in emergency treatment, hospitalisation, or treatment with systemic corticosteroids
- E4. Reduced lung function: FEV₁ <70% of predicted value after adequate pharmacologic treatment¹³
- E5. SLIT treatment with any grass pollen AIT for more than 1 month within the last 5 years. In addition, any SLIT treatment with grass pollen AIT within the previous 12 months
- E6. SCIT treatment with any grass AIT reaching the maintenance dose within the last 5 years. In addition, any SCIT treatment with grass AIT within the previous 12 months
- E7. Ongoing treatment with any allergy immunotherapy product
- E8. Uncontrolled or severe asthma requiring daily use of more than 800 mcg budesonide or equivalent at screening
- E9. Severe chronic oral inflammation
- E10. Any nasal or naso/oropharyngeal condition that could confound the efficacy or safety assessments (e.g. hypertrophy of the pharyngeal/palatine tonsils, clinically relevant nasal polyps, a history of paranasal sinus surgery or surgery of nasal turbinates)¹⁴
- E11. Has a diagnosis of eosinophilic oesophagitis
- E12. At randomisation, current symptoms of, or treatment for, upper respiratory tract infection, acute sinusitis, acute otitis media or other relevant infectious process (serous otitis media is not an exclusion criterion)
- E13. A relevant history of systemic allergic reaction e.g. anaphylaxis with cardiorespiratory symptoms, generalised urticaria or severe facial angioedema that in the opinion of the investigator may constitute an increased safety concern
- E14. Any clinically relevant chronic disease incl. malignancy that in the opinion of the investigator would interfere with the trial evaluations or the safety of the subject
- E15. Active or poorly controlled autoimmune diseases, immune defects, immunodeficiencies, immunosuppression or malignant neoplastic diseases with current disease relevance

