8 TRIAL PRODUCTS

8.1 IMP

The IMP provided in this trial is 5-grass mix SLIT-drops or placebo.

All IMPs are manufactured and provided by ALK. The placebo is similar to the active treatment with regards to appearance, smell and taste.

Please refer to **Table 3** and the Trial Supplies Catalogue provided by ALK for details regarding IMP and background treatment.

IMP name:	Active treatment	Placebo
	5-grass mix SLIT-drops	
Active ingredients:	Allergen extracts from the five grass	None
	species:	
	Dactylis glomerata L (cat grass /cock's	
	foot/orchard grass),	
	Phleum pratense L. (timothy grass), Lolium	
	perenne L. (perennial rye-grass),	
	Anthoxanthum odoratum L (sweet	
	vernal/vernal grass),	
	Poa pratensis L. (Kentucky	
	bluegrass/meadow grass)	
Dosage form:	SLIT-drops	SLIT-drops
	Sublingual solution	Sublingual solution
Excipients:	Glycerol, carbonate, sodium chloride	Glycerol, carbonate, sodium chloride
Route of	Sublingual	Sublingual
administration:		
Dose/strength:	Initiation:	N/A
	50 SRU/day for five consecutive days	
	followed by 150 SRU/day for five additional	
	consecutive days.	
	Maintenance:	
	300 SRU/day from day 11.	
Dosing instruction:	One single-dose container (0.5 ml) once	One single-dose container (0.5 ml)
	daily.	once daily.
	First dose will be dispensed at site at visit 2	First dose will be dispensed at site at
	(randomisation visit)	visit 2 (randomisation visit)

Table 3 IMP details

Each subject will be randomly assigned to receive active treatment or placebo.

IMP dispensing

The treatment will start at visit 2 (randomisation visit). Hereafter, IMP will be dispensed at visits 3-8. The first dose will be administered under medical supervision for at least 30 minutes after intake.

8.2 **Rescue medication**

During the trial, subjects may experience allergy symptoms that require additional treatment. Rhinoconjunctivitis pharmacotherapy for allergic rhinitis or conjunctivitis will be provided by the
Clinical trial protocol	Date:	12-Nov-2021	
Trial ID: SU-G-01	Version:	4.0	
EudraCT No. 2020-000455-12	Status:	Final	
CONFIDENTIAL	Page:	36 of 77	

sponsor to subjects as pre-defined, open-labelled rescue medication and may be used in addition to the IMP to which the subjects have been randomised if needed.

For the rhinoconjunctivitis symptoms the subject will be provided with:

- Oral antihistamine tablets (Desloratadine, 5 mg)
- Nasal corticosteroid spray (Mometasone furoate, 50 µg/dose)

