9.2 Precautions in relation to first dosing

The first intake of IMP should be at the clinic with a subsequent 30 minutes observation period. An oropharyngeal examination should be performed prior to the first IMP dosing and should be repeated after 30 minutes.

For subjects with severe oral inflammation (e.g. oral lichen planus, mouth ulcers or thrush), oral wounds or following oral surgery, including dental extraction or following tooth loss, initiation of IMP treatment should be postponed to allow healing of the oral cavity.

For subjects with symptoms of or in treatment for upper respiratory tract infection, acute sinusitis, acute otitis media or other relevant infections, initiation of IMP treatment should be postponed until the condition has improved. If first dosing is postponed, the first intake of IMP should still be at the clinic with a subsequent 30 minutes observation period.

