11.8 Physical examination

The physical examination should be performed by a physician and should be based on the body systems as described in **Table 5**.

Body system	Minimum examinations to be completed
General appearance	As applicable
Skin	Inspection of skin
Head (ears, eyes, nose and throat)	Ears - Inspection of auricles and external canal (otoscopy is not required) Eyes - Inspection of conjunctivae and eyelids, examination of pupils including reaction to light Nose - Inspection of nasal mucosa Oral cavity - oropharyngeal inspection of lips, tongue, tonsils and uvula will be performed for signs of mouth irritation, oedema, and any other abnormalities. Oropharyngeal inspection is performed before and after administration of IMP at randomisation V2 and as per investigator discretion during the trial
Respiratory	Auscultation/stethoscopy of the lungs
Heart	Auscultation/stethoscopy of the heart
Lymph nodes	Examination of lymph nodes (cervical, axillary, and inguinal lymph nodes)
Abdomen	
Urogenital	
Musculoskeletal and neurological	If applicable
Other abnormality	

Table 5Physical examination

Physical examination of optional body systems not performed should be marked as not done (ND) in the eCRF.

Clinical trial protocol	Date:	12-Nov-2021	
Trial ID: SU-G-01	Version:	4.0	
EudraCT No. 2020-000455-12	Status:	Final	
CONFIDENTIAL	Page:	43 of 77	

Significant findings that are present at screening must be recorded as medical history in the eCRF. Significant findings found at the following visits, which meet the definition of an AE, must be recorded on an AE page in the eCRF.

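### SAP 6.4.1 counts treatment duration, and the compliance denominator, from randomisation, although Protocol 9.2 allows a later first dose

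*SAP*

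**What the plan says.** SAP 6.4.1 (Extent of exposure) defines three linked quantities.

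- **Duration:** "The duration of treatment for each subject will be calculated from the date of randomisation", up to and including the last IMP intake.
- **Compliance:** it "will be assessed as the number of doses taken divided by the treatment duration multiplied by 100", with a cap at 100%.
- **Doses taken:** doses dispensed minus doses returned. On returns, the SAP says: "Returned doses were counted by counting unopen foil bags and multiplying by number of doses in a bag". A bag holds five doses.

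Protocol 8.1 places the first dose at visit 2, the randomisation visit. Protocol 9.2 provides for exceptions. They cover severe oral inflammation (ulcers and thrush are among its examples) and also "oral wounds or following oral surgery, including dental extraction or following tooth loss, initiation of IMP treatment should be postponed to allow healing". It adds: "If first dosing is postponed, the first intake of IMP should still be at the clinic". It sets no maximum delay.

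Elsewhere the SAP works from the first dose. It does so in the definition of a treatment-emergent adverse event (sections 2 and 6.4.2.1), in the imputation of partial adverse event start dates (9.4.1), and in the summary of onset in minutes on the first day of treatment (6.4.2.2).

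**The concern.** The duration interval ends on an intake date but starts on an allocation date. When the first dose is postponed, the days in between are reported as time on treatment. Because the same interval is the compliance denominator, those days also count as missed doses, although the subject followed the protocol.

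This can happen to a validly randomised subject. The only oral exclusion, E9, is "Severe chronic oral inflammation". E12 concerns respiratory, sinus, ear and other relevant infections at randomisation. Thrush might be argued into E12; wounds, oral surgery, extraction and tooth loss cannot. The problem can also come to light on the day of randomisation itself, because Table 5 of Protocol 11.8 says: "Oropharyngeal inspection is performed before and after administration of IMP at randomisation V2".

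What is at stake is the accuracy of the exposure and compliance summaries, and their consistency with the adverse event tables. For a postponed subject, treatment duration and the treatment-emergent period in the same report would start on different days. Doses taken are not affected. Nor are the type I error, the power, the primary estimate or any analysis set, and under blinding no difference between arms is expected.

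**Working it through.** The plan gives no figure for compliance, duration or frequency of postponement, so there is nothing to reproduce.

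**Inputs from the documents**
- One dose per day (Protocol 9.1).
- Planned treatment of about 26 months (Protocol 3.1): 26 × 365.25/12 = 791 days.
- Last subject randomised 31-Dec-2021, last subject last visit 22-Sep-2023 (SAP Table 1): 630 days apart, the longest possible duration for that subject.
- Seven accountability visits, V3 to V9, and five doses per bag (SAP 6.4.1).

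**Assumptions (not in the documents)**
- Delay d from randomisation to first dose: 7 to 28 days.
- Early stop, as an example: 90 days after randomisation.
- Share of subjects postponed: 1% to 5%.

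**Step 1: no counting offset.** Let D be the days from randomisation to last intake. A subject who takes every dose from the first intake takes D − d doses. The SAP rule gives 100 × (D − d)/D; starting at first intake gives 100 × (D − d)/(D − d) = 100%. The understatement is 100 × d/D points, and duration is too long by d days.

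| D (days) | d = 7 | d = 28 |
|---|---|---|
| 791 (planned 26 months) | 7/791 = 0.9 points | 28/791 = 3.5 points |
| 630 (last subject randomised) | 7/630 = 1.1 points | 28/630 = 4.4 points |
| 90 (assumed early stop) | 7/90 = 7.8 points | 28/90 = 31.1 points |

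**Step 2: offset from bag counting.** Unused doses in an opened bag count as taken. With at most one part-used bag per accountability visit, that is 0 to 4 doses at each of 7 visits, so o = 0 to 28 doses. Reported compliance is min(100, 100 × (791 − d + o)/791):

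| d | o | Reported compliance |
|---|---|---|
| 28 | 0 | 763/791 = 96.5% |
| 28 | 14 | 777/791 = 98.2% |
| 28 | 28 | 791/791 = 100% |
| 7 | 0 | 784/791 = 99.1% |
| 7 | 14 | 798/791, capped at 100% |

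Starting at first intake, the value is 100% in every row. The net understatement over 791 days is therefore 0 to 3.5 points. The offset does nothing for duration, which stays too long by d.

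**Step 3: arm mean, before offset.** Compliance moves by 1% × 0.9 = 0.01 points at the low end and 5% × 3.5 = 0.18 points at the high end. Mean duration moves by 1% × 7 = 0.07 days to 5% × 28 = 1.4 days.

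**The case against.** The strongest reply is that the two dates coincide by design. Protocol 8.1 puts the first dose at visit 2, the flow chart marks clinic intake only there, and the SAP reports 445 subjects randomised and dosed without mentioning any postponement. A site could also reschedule visit 2, since no maximum interval from screening is stated, and then both dates would move together.

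The affected group may indeed be empty; the documents do not say. Rescheduling visit 2 is possible, but it is not what Protocol 9.2 describes. That section postpones IMP initiation and first dosing, not randomisation. Its instruction that a postponed first intake must still be at the clinic would be redundant if the whole visit moved, because visit 2 already includes clinic intake.

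A second reply is that the sizes are assumed. The only healing interval in the documents is the 7 days that Protocol 9.4 allows for interruptions, which is the bottom of the assumed range. At 7 days a full-term subject loses 0.9 points, and seven unused doses in opened bags would cancel that. The 31-point figure combines the longest assumed delay with an early stop. This is fair, and it keeps the point small. It does not restore the duration, which bag counting cannot correct.

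Finally, no decision rests on these tables, since SAP 6.5 removed the per-protocol set, and the compliance measure is already coarse. Both statements are right. They limit the importance of the point but do not justify counting undosed days as treatment.

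**Conclusion.** The concern holds, as a minor one. For any eligible subject whose first dose is postponed, the SAP rule overstates treatment duration by the full delay and lowers compliance by up to the delay divided by the duration.

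Under the assumed 7 to 28 days, a full-term adherent subject loses 0 to 3.5 points once bag counting and the cap are allowed for. Early discontinuers could lose more, and arm means would barely change. If no subject was postponed, nothing changes. The consequences are confined to descriptive summaries.

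**What to change.** In SAP 6.4.1, calculate treatment duration from the date of first IMP intake up to and including the date of last IMP intake, and use that duration as the compliance denominator.

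This changes one derivation. It needs no new data: SAP 9.4.1 already uses the date of first dose, and SAP 3.2 states that all 445 randomised subjects were dosed. Values for subjects dosed on the day of randomisation stay the same. The change can be made before database lock; if made later, Protocol section 15 already provides for documenting it in the trial report.

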Primary trial completion date	Date of the last data collection for the primary endpoint (ClinicalTrials.gov) is the last scheduled physical visit for any subject (V9).
Rescue medication	Medicinal products provided by ALK when the efficacy of the IMP is not sufficient or likely to cause an AE to the subject or to manage an emergency situation in relation to grass pollen allergy symptoms in agreement with the EMA Definition of IMPs and Use of AMPs Consultation Document (EMA 2016)
	The rhinoconjunctivitis rescue medication in this trial is:
	Antihistamine tablets
	Antihistamine eye drops
	Corticosteroid nasal spray.
Source documents	Source documents are original documents, data, and records from which the subjects' electronic case report form (eCRF) data are obtained. These include, but are not limited to, hospital records (from which medical history and

	concomitant medication may be summarised into the eCRF), clinical and office charts, laboratory and pharmacy records, diaries, microfiches, radiographs, and correspondence.
Systemic corticosteroids	Oral, intramuscular, or intravenously administered corticosteroids.
TEAE	TEAEs are defined as AEs with start date and/or time on or after the time of first IMP administration and no later than 7 days after last IMP administration.
Trial completion	The trial is completed once the CSR is signed.
Withdrawal from trial date	Date of subject withdrawal from trial. In case of subjects lost to follow-up, the withdrawal date is defined as the date the investigator/sponsor decides to withdrawal the subject.

3 Introduction

The SAP supplements the statistical section in the protocol and provides additional details regarding estimands, analysis sets, endpoints and statistical analyses. In Section 9.1 detailed descriptions of pollen seasons, derivation of endpoints, imputation of dates, and the statistical analyses are provided. In supplementary document to the SAP: Documentation of Trial Analysis Sets, the various subject related listings are provided.

Changes to the analyses and changes that might (or can) impact the analyses described in the protocol are documented in Section 6.5.

This SAP has been written and approved before database lock and unblinding.

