8.3 Subject disposition

Subject disposition will be summarised by number and percentage of subjects screened, randomised and not treated, randomised and treated, included in the analysis sets, completed trial, withdrawal from the trial, reason of withdrawal of trial, completed IMP, discontinued IMP, and reason for IMP discontinuation by treatment group and total. Some endpoints will be also summarised by year. In addition, the reasons for discontinuation of IMP following the estimand framework will be summarised by treatment groups and total.

IMP discontinuations over time by different reasons will be visualised by a band plot showing proportions on treatment, having discontinued treatment due to AE, withdrawal by subject, and all other reasons (pooled).

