9.4 Imputation of dates

9.4.1 Partial dates in AE reporting

Partial dates and time for start of AEs will be imputed as follows:

- Missing day will be imputed as maximum of first day of month and day of first IMP dose.
- Missing month will be imputed as maximum of first day in January and date of first IMP.
- Missing time is calculated as the first minute of the day (i.e. if the AE start date is 16-AUG-2022 then the AE start datetime will be 16-AUG-2022 T:00:00)

Partial dates and time for end of AEs will be imputed as follows:

- Missing day will be imputed as minimum of last day in month and day of last contact.
- Missing month will be imputed as minimum last day of December and date of last contact.
- Missing time is calculated as the last minute of the day (i.e. if the AE end date is 16-AUG-2022 then the AE start datetime will be 16-AUG-2022 T:23:59)

With these imputation rules, AEs will be considered TE when dates are partial and the existing information does not exclude the possibility of the event being treatment-emergent.

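### Treatment duration and the compliance denominator in SAP 6.4.1 start at randomisation rather than at first IMP intake (minor; descriptive tables only)

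*SAP*

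**What the plan says.** SAP 6.4.1 (Extent of exposure) sets three linked rules:

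- Duration is "calculated from the date of randomisation up until and including the date of the last IMP intake".
- Compliance uses that duration as its denominator: "IMP compliance (%) will be assessed as the number of doses taken divided by the treatment duration multiplied by 100".
- The numerator is doses dispensed minus doses returned. "Returned doses were counted by counting unopen foil bags and multiplying by number of doses in a bag" (five doses per bag). Lost doses are not taken into account, and "thus IMP compliance will be capped to 100" per cent.

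Protocol 8.1 plans the first dose at visit 2, the randomisation visit. Protocol 9.2 provides for exceptions. In severe oral inflammation, with oral wounds, or after oral surgery, "including dental extraction or following tooth loss, initiation of IMP treatment should be postponed to allow healing of the oral cavity". A similar instruction covers respiratory and other infections. Section 9.2 adds that a postponed first intake must still take place at the clinic under observation. It gives no maximum delay.

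Elsewhere the SAP anchors exposure on the first dose. Its table of definitions requires TEAE onset "on or after the time of first IMP administration and no later than 7 days after last IMP administration". For partial AE start dates, 9.4.1 says: "Missing day will be imputed as maximum of first day of month and day of first IMP dose".

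**The concern.** Treatment duration should describe time on treatment. If it starts at randomisation, every day between randomisation and first intake is counted as a treated day in the duration table and as a day with a dose due in the compliance table. A subject whose first dose was held back on the protocol's instruction would then look exposed for longer and less adherent than was the case.

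Within one safety report, the AE tables would start exposure at first dose while the duration and compliance tables started it at randomisation. Only those two descriptive summaries are at stake.

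**Working it through.** The plan states no duration or compliance figure to reproduce, so the check has two parts: whether the dates can differ, and how large the error is when they do.

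**Can the dates differ?** Protocol 4.2 closes part of the route. E12 bars subjects with a current infection at randomisation, so the infection clause of 9.2 mostly delays randomisation itself. E9 bars severe oral inflammation only if it is chronic. An acute mouth ulcer, an oral wound or a recent dental extraction is barred by neither, yet 9.2 requires the first dose to wait. Such a subject can be randomised at visit 2 and dosed later.

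**Formulas.** Let D be the duration as the SAP counts it (randomisation to last intake, inclusive), k the days from randomisation to first intake, and e the untaken doses that bag counting credits as taken. For a subject who misses no dose after starting:

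- correct duration = D − k
- relative overstatement of duration = k / (D − k)
- SAP compliance = min(100%, (D − k + e) / D); the correct value is 100%

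**Range for D.** Individual dosing dates are not given, so these are assumptions.

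- Short end: last randomisation 31 Dec 2021 (SAP Table 1) to the earliest 2023 EGPS stop in SAP Appendix B, 1 Jul 2023: 548 days.
- Long end: 15 Aug 2021 to the latest 2023 EGPS stop, 26 Aug 2023: 742 days. SAP 3.2 prints the first randomisation as 15-Aug-2022, which falls after the last randomisation; the year 2021 is assumed here.

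**Results with e = 0** (k is also an assumption):

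| k | D | Duration overstated by | SAP compliance |
|---|---|---|---|
| 14 | 548 | 14/534 = 2.6% | 534/548 = 97.4% |
| 14 | 742 | 14/728 = 1.9% | 728/742 = 98.1% |
| 28 | 548 | 28/520 = 5.4% | 520/548 = 94.9% |
| 28 | 742 | 28/714 = 3.9% | 714/742 = 96.2% |

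Early discontinuers are affected more. With 30 days of complete dosing after a 14-day delay, compliance is 30/44 = 68.2% instead of 100%.

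**Masking by bag counts.** Only unopened five-dose bags count as returned, so an opened bag can credit 0 to 4 untaken doses at each of the seven accountability visits (V3 to V9). That gives e between 0 and 4 × 7 = 28. Whenever e ≥ k, compliance reaches the 100% cap and the error disappears from view. The duration error stays at k days whatever e is.

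**Arm level.** If a share p of subjects is delayed by 14 days, mean duration rises by 14p days and mean compliance falls by at most p × 14/D. For an assumed p of 1% to 5%:

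- duration: 14 × 0.01 = 0.14 days to 14 × 0.05 = 0.70 days
- compliance: 0.01 × 14/742 = 0.02 percentage points to 0.05 × 14/548 = 0.13 percentage points

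**Where the quantities are used.** SAP 6.4.1 only summarises duration and compliance by treatment group. The per-protocol set, the natural place for a compliance threshold, was removed (SAP 6.5).

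**The case against.** The strongest reply is that the error may never occur. Visit 2 is the planned first-dose day, and the protocol flow chart marks clinic intake at that visit only. Section 9.2 does not say that the postponement follows randomisation. A site could comply by moving visit 2, since the flow chart shows only a minimum interval after screening. The requirement of at least 16 weeks of treatment before the first season also limits how long a delay can be. All of this is fair. That the gap falls after randomisation is an inference from 9.2 and the exclusion criteria, and nothing shows that any subject had one. But moving visit 2 is only one way to comply, and the provision for a postponed first intake at the clinic foresees a separate dosing occasion.

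A second reply is that the SAP's other sections do not prove that the dates differ. The disposition table in 8.3 does list "randomised and not treated, randomised and treated", but that concerns whether a subject was ever dosed, and SAP 3.2 says all 445 were randomised and dosed. The TEAE rule needs the time of first dose even when both events fall on one day. Both points stand. What remains is that the first-dose date is already required, so using it costs nothing.

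A third reply is that Appendix B gives pollen dates, not dosing dates. Taking the last subject's last visit, 22 Sep 2023, as the end would lengthen the long end to 769 days and give 755/769 = 98.2% for a 14-day delay. The picture does not change.

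**Conclusion.** The concern holds, as a minor point. The rule in SAP 6.4.1 is wrong for any subject first dosed after randomisation, a situation the protocol makes possible. Such a subject's duration is overstated by exactly the delay. For an otherwise fully adherent subject with a 548- to 742-day duration, compliance falls by about 2 to 3 percentage points for a 14-day delay and 4 to 5 for a 28-day delay, before any masking by bag counts and the cap.

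These sizes rest on assumed delays and durations. The number of affected subjects is unknown, and if it is zero the tables are unaffected. Effects on arm means are negligible under the shares assumed. No estimand, hypothesis test, TEAE definition or analysis set is affected.

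**What to change.** In SAP 6.4.1, define treatment duration as running *from the date of first IMP intake* to the last intake inclusive, that is, last intake date minus first intake date plus one. The compliance denominator follows without further change. No protocol amendment or additional table is needed.

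The cost is one phrase and no new data. If the SAP can no longer be revised, the change can be recorded in the clinical trial report, as protocol section 15 provides. The one consequence is that a late start no longer lowers compliance. That is appropriate, because a postponement under 9.2 is not non-adherence.
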